1.0 Objectives*

- As a pain psychologist and palliative care researcher, I developed 1. develop a novel mHealth intervention that harmonizes psychological and pharmacological support for advanced cancer pain. I adapted core components of pain-CBT and integrated them into STAMP (Smartphone Technology to Alleviate Malignant Pain), an existing NINR-funded cancer pain mHealth intervention. STAMP enables patients with advanced cancer to track their pain, opioid use, and side effects. It delivers tailored education and self-management advice while facilitating clinician monitoring and patients' proactive outreach. Having developed an extensive suite of multi-media cancer pain psycho-education covering core pain psychology principles, I seized a strategic opportunity to refine and integrate pain-CBT treatment into medically oriented self-management support in STAMP. Capitalizing on mHealth technology, I strove to destignatize pain psychology through a potentially scalable model that can disseminate behavioral treatments for advanced cancer pain paired with their palliative care pain management plan. My aim is to:
 - Determine feasibility and acceptability of the STAMP+CBT app: up to 15 patients with advanced cancer pain will be recruited from outpatient palliative care clinics at a major cancer center to participate in a single-arm, 6week study of STAMP+CBT (4-week intervention period and a 2-week post intervention period). Surveys at baseline, 4 weeks (end of intervention period), and 6 weeks (end of 2-week post intervention period) will explore trends in pain specific intensity, self-efficacy, and catastrophizing, physical function, opioid use, and quality of life. End-ofstudy interviews will identify facilitators and barriers to usability, acceptability, and satisfaction of the app. The primary outcome will be feasibility evaluating 1) app retention rates and 2) completion of app exercises.

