8.0 Study Endpoints*

8.1 ENDPOINT 1: The primary objective is to determine feasibility and acceptability of STAMP+CBT. Specifically, we will evaluate patients' adherence to daily and weekly comprehensive symptom selfassessments within the STAMP+CBT app. We will calculate patients' overall adherence rate and 95% confidence interval. Defined using precision analysis, we will consider the intervention to be feasible if >70% of subjects complete >4 of the 6 pain-CBT modules and completes 50% of surveys by the end of 4 weeks (completion of the 4week intervention study period; completion of the 2-week post intervention period will be exploratory).^{40,41} The intervention will be considered **acceptable** if >80% of the acceptability items are rated 4 or higher/5; lower ratings will lead to app refinements. Other feasibility measures will assess time to accrual, participation rates, study retention and completion rates, and the number of patients who continue to review app content between weeks 5-6 (post-intervention period). Power calculation: With 10 patients, we will be able to estimate these proportions with margins of error (half of a 95% confidence interval) of approximately 18% or less assuming that the feasibility threshold of 70% is reached. This margin of error is small enough so that proportion estimates relevant to study feasibility will be

accurate and provide informative guidance for future, larger studies. Using **qualitative** framework analysis methods, we will explore barriers/facilitators, suggested changes to content, acceptability of intervention engagement, and whether app use continues after completion. Although power is not sufficient in this pilot, we will explore associations between levels of engagement and changes in pain severity/interference, opioid use, catastrophizing, sleep, mood, and pain self-efficacy.

8.2 COMPREHENSIVE ENDPOINT: The study team will use qualitative and quantitative results to determine the feasibility and acceptability of this pain CBT mobile health app for patients with cancer. This feasibility study will inform final modification to the application and study procedures in preparation for a future efficacy study of the STAMP+ CBT mobile health app.

9 Procedures Involved*

9.1 STUDY PROCEDURES:

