The content for the STAMP+CBT application can be reviewed and referenced in appendices D, F, Y, Z. Once app programming is completely finalized, patients in the Pilot Cohort will engage in the pilot study to evaluate app feasibility and acceptability.

- 9.2 Patients in the Pilot Cohort will pilot the application for 4 weeks (or 6 weeks if they request to review the content further, this will allow us to test the correct length of app use). The onboarding and monitoring protocol is available in Appendix S. In addition, the RA will contact participants after 4 weeks (end of intervention period), and 6 weeks (end of 2-week post-intervention period). The purpose of these contacts would be to schedule the end of intervention interview and confirm completion of survey assessments, as well as the final survey assessments at 6 weeks (end of 2-week post-intervention period).
- 9.3 Participants will fall into only one eligibility category:

Pilot Cohort = Patient pilot testing

Description	Components of Participation

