Participants will include DFCI patients presenting to outpatient palliative care, GCC, or satellite (MV and LD) clinics with ongoing chronic cancer pain management issues. Participants will meet with the study team in person, over the phone, or via a compliant and secure video chat/screen- share platform (i.e. Zoom). We will conduct the pilot cohort with up to 15 patients. Each participant will receive a \$25 gift card upon completion of the 4-week intervention period, and another \$25 gift card upon completion of the 2-week post intervention survey. The first 5 patients will onboard to the application and their involvement/feedback will focus on making final revisions onboarding for the application and study procedures. Therefore, the following 10 patients' data will be included for pilot study analysis and feasibility findings.	 Use the STAMP+CBT mobile app for 4 weeks (intervention period, 4 weeks for content introduction, extended 2 weeks for review of content if patient's request this) Engage with pain CBT content including a goal-setting module, relaxation exercises, and educational content Daily and weekly reporting of pain, catastrophizing, mood, and sleep symptoms and painkiller usage and satisfaction through the app (Appendix U) Complete survey assessments at baseline, 4 weeks (end of intervention period), and 6 weeks (end of 2-week post intervention period) assessing pain severity, self-efficacy and catastrophizing, physical function, opioid use, and quality of life outcomes. (Appendices P, Q, R) End-of-intervention interview (4 weeks) assessing usability and acceptability (Appendix T)
	• Wedical Record Abstraction (Appendix O)

 Table 1. Brief description of pilot cohort activities

PILOT COHORT:

The first few patients (up to 5) will onboard to the application and their involvement/feedback will focus on making final revisions to the mobile application and study procedures. All procedures will be the same for the 15 patients, however, data for the initial patients (up to 5) will not be included in final analysis as their involvement will be focused on revising final app bugs/iterations and modifications to study procedures before the pilot trial initiation. The following patients (up to 10) will be considered as the core pilot study participants to evaluate feasibility and acceptability of the application and study procedures.

Survey assessments

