An RA will ask the patient to complete a baseline survey assessment after consenting, at the end of the 4-week intervention study period, and at the end of the 2-week post intervention period to assess key outcomes (pain severity/interference,⁴² QOL⁴³), potential mediators of intervention effects (catastrophizing⁴⁴, self-efficacy⁴⁵, perceived stress⁴⁶, anxiety/depression⁴⁷, sleep⁴⁸), acceptability,⁴⁹ and usability⁵⁰. The survey can be completed remotely though a link to a Partners Healthcare compliant electronic survey system (e.g. REDCap), over the phone with the RA, over Zoom with the RA,

in person with pen and paper or on a tablet. The Baseline survey will assess socio-demographics, barriers to pain management, pain severity, opioid use, pain and psychological symptoms, and quality of life, with metrics shown in Table 5. End of 4-week intervention period survey will largely replicate the baseline survey; additionally, patients will rate their satisfaction with STAMP+CBT using the 6-item Acceptability E-scale. Surveys will be used to assess pain and psychological symptom trajectory, medication use, and quality of life. See **Appendix P** for the Baseline survey items, **Appendix Q** for 4-week (end of 4-week intervention period) survey items, and **Appendix R** for 2-week (post intervention period) follow-up survey items. Additionally, a subset of patients (up to 10) will be invited for a qualitative interview focused on study burden, facilitators/barriers to app use, satisfaction, and perceived utility in order to guide future refinements to the app (see Appendix T) when they complete use of the app at 4 weeks (end of intervention study period).

Intervention

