After the patient completes the baseline survey, the RA will meet with the patient (in person or virtually), to assist in either 1) downloading the application onto participants' mobile device or 2) providing/mailing the study phone to the participant. The RA will help to register the patient to the app and help set up any preferences. The RA will then conduct a 15-minute tutorial on the STAMP+CBT app and its intended use (Appendix S). The RA will also input the patient's pain medications from Epic, reconciling this list with the patient, and with the nurse navigator on the patient's care team if there are any discrepancies. As the nurse navigator is already a member of the care team, they'll have access to all Epic records and any documentation for this study included in Epic. The participant will also input their desired goal to work towards for the duration of the trial. During the trial, there is also a function in the app that allows participants to notify the research team if a medication or goal needs to be changed and reflected in the app. Final iterations to the app, research portal, and study procedures will be made following the initial few patients (up to 5) recruited to using the application. Thereafter, we will begin recruiting patients (up to 10) for the pilot study cohort.

Participants will utilize STAMP+CBT for 4-weeks (intervention study period). The 4 weeks will consist of all content introductions. Patients will also be offered the opportunity to continue their app use for the next 2 weeks (post-intervention period) until study completion (2 week follow up and survey), this will allow us to assess feasibility and acceptability of the appropriate length of use for the intervention. STAMP+CBT hosts and organizes patients' opioid/non-opioid analgesics. It has an extensive multi-media library of education content related to pain management (Appendix C)

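### The acceptability part of the length-of-use aim for optional weeks 5-6 rests on indirect evidence: no acceptability or usability measure is clearly scheduled after week 4

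*Combined protocol and SAP*

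**What the plan says.** **Purpose of weeks 5-6.** Section 9.2 allows six weeks of use instead of four for patients who ask to review content further, and says "this will allow us to test the correct length of app use". Section 9.3 (Intervention) says of the same two weeks that "this will allow us to assess feasibility and acceptability of the appropriate length of use for the intervention". Section 8.1 includes among the topics of the qualitative analysis "acceptability of intervention engagement, and whether app use continues after completion".

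**Timing of the acceptability and usability measures.** In section 9.3 (Survey assessments), the account of the 4-week survey says "additionally, patients will rate their satisfaction with STAMP+CBT using the 6-item Acceptability E-scale". Table 1 lists "End-of-intervention interview (4 weeks) assessing usability and acceptability (Appendix T". The survey text says that up to 10 patients will be invited to interview "when they complete use of the app at 4 weeks (end of intervention study period". Table 5 marks Satisfaction and Usability (SUS) at T2 (week 4) and leaves T3 (week 6) blank. Section 9.6 describes the week-6 survey as covering quality of life, pain, psychological measures, healthcare utilization and app use.

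**Looser statements.** The opening sentence of Survey assessments covers baseline, week 4 and a survey "at the end of the 2-week post intervention period to assess key outcomes", and its list goes on to include acceptability and usability. Section 1.0 says that at the end of the study "interviews will identify facilitators and barriers to usability, acceptability, and satisfaction of the app". Section 9.4 also labels the interviews end-of-study.

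**The concern.** The extension is given a job: to inform how long the app should be used. Under the specific schedule, patients give their views on acceptability and usability when the first four weeks end, before they have experienced the extra two. An interview at that point cannot establish whether use continued afterwards, although section 8.1 assigns that topic to the qualitative analysis.

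Section 8.2 says the pilot will inform final changes to the app and procedures before an efficacy study, and length of use is one such choice. Without patients' own ratings or reasons, the team would have to infer acceptability of the longer period from who kept opening the app.

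**Working it through.** No figure in the plan is at issue. The check sets the aim beside the measurement schedule.

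1. **The aim has two halves.** Section 9.3 names both feasibility and acceptability of the length of use, so each needs its own check.

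2. **Feasibility half: data are planned.** Section 8.1 counts patients who go on viewing content in weeks 5-6. Table 5 collects use of STAMP+CBT at T3 and from app data, and section 9.6 puts app use in the 6-week survey. No threshold is attached.

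3. **Acceptability half: sources and timing.**
   - Acceptability E-scale: described as an addition to the 4-week survey; Table 5, Satisfaction, T2 only.
   - SUS: Table 5, T2 only.
   - Interview: week 4 in Table 1 and in Survey assessments.
   - Sources clearly scheduled after week 4: 0 of 3.

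   Section 9.5.2 also mentions an acceptability survey after review of the content, but gives no week. All content is introduced within the four weeks (section 9.3, Intervention), so this does not point to week 6.

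4. **Is the blank at T3 a slip?** Table 5 marks T3 for measures that are repeated at week 6, such as the BPI, FACT-G and PCS. Section 9.6 also omits acceptability and usability. The two places agree.

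5. **Does the sentence on all three surveys override this?** It covers baseline too, when no patient has used the app and none could rate it. It cannot be a literal schedule. If week-6 ratings were intended, Table 5 and section 9.6 need correcting instead.

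6. **What continuation can show.** A patient may stop because of illness, because all content has been seen, or because the app was unwelcome. A count does not separate these. Its denominator is also unclear: section 9.2 and Table 1 extend use at the patient's request, whereas section 9.3 (Intervention) says patients will be offered it.

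7. **Extent.** The period concerned is 2 of the 6 weeks of participation. Up to 10 patients are analysed, because the first patients (up to 5) are excluded from the final analysis.

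**The case against.** A reader might infer that the length-of-use question cannot be answered at all, or that any statement about six weeks would rest on no data. The documents do not support that. The continuation count, app logs and T3 app-use items serve the feasibility half, and voluntary continuation bears indirectly on acceptability.

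A reader might also infer that every acceptability instrument is certain to be finished before week 5. That is not established either. Under section 9.2 the research assistant contacts patients after week 4 and again at week 6, and these contacts serve partly to schedule the interview. An interview booked at the first contact could fall within weeks 5-6. The end-of-study label in sections 1.0 and 9.4 points the same way. Appendices R and T are not in the available text, and either may already ask about length. A patient who has seen all the content by week 4 can also say whether four weeks was enough.

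On importance, length of use is a rationale for an optional extension, not a numbered endpoint. Section 8.1 calls completion of the post-intervention period exploratory (the parallel sentence in section 11.2 does not repeat that label). Neither the feasibility rule nor the criterion that more than 80% of acceptability items be rated 4 or higher out of 5 needs ratings from weeks 5-6. Finally, a week-6 scale given to everyone would mix patients who continued with those who stopped.

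Most of this stands, and it limits the point to the acceptability half. It does not remove the gap. A view given at week 4 is a preference, not experience of the extra weeks, and the specific passages on timing agree with one another. The mixing of patients is met by reporting the two groups separately.

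**Conclusion.** The point holds in a limited form. The feasibility of the longer use has planned, exploratory data. Its acceptability has only indirect evidence from continuation, because none of the three acceptability or usability sources is clearly scheduled after week 4. The plan therefore cannot be relied on to show why patients continued or stopped, or how they found the longer period.

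This rests on three assumptions: that Table 5, section 9.6 and the week-4 interview label govern over the looser wording; that the Satisfaction row of Table 5 (labelled a novel metric) is the Acceptability E-scale named in the text; and that Appendix R does not already contain such items.

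The primary feasibility result and the acceptability criterion are not affected. The change is worth making because it is cheap and lets the pilot address a question that it sets itself.

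**What to change.** - **Add to the existing 6-week survey** (Appendix R; mark T3 for Satisfaction in Table 5), unless already there: the 6-item Acceptability E-scale, one item on whether the length of use was too short, right or too long, and one on the reason for continuing or stopping.
- **Report these as exploratory**, separately for patients who continued and those who stopped at week 4. With at most 10 patients across both groups, give counts only.
- **Keep the week-4 rating for the criterion of more than 80%**, and say so. Sections 8.1 and 11.2 attach no time point to it.
- **Reconcile the timing statements**: the list for all three surveys in section 9.3, and the end-of-study interview label in sections 1.0 and 9.4, with Table 5 and the week-4 interview. State also whether the extension is offered to everyone or given on request.
- **If no items are added**, limit the claims in sections 9.2 and 9.3 to describing continued use.

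Cost: 6 + 2 = 8 extra items at week 6, a small added burden for patients. The survey and the week-6 contact are already planned, so no new visit is needed.

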9.4 MONITOR SUBJECTS FOR SAFETY AND MINIMIZE

RISKS: The risks to participants in the Pilot Cohort are minimal. The primary risk is loss of confidentiality/privacy. To monitor the risk of loss of confidentiality/privacy, the study team has ensured that the STAMP+CBT app is HIPAA compliant and meets the privacy and security standards set by DF/HCC, and will continue to do so with modifications in this study (IT approval received from [name]). In addition, all collected study data will be maintained in a secure location and personal identifiers will be removed. As described above, end of study interviews will be audio and video recorded, and transcribed for analysis of participant feedback. For the patients engaging in qualitative interviews, their video recorded data will be destroyed after manuscript publication.

Risks to participants in the Pilot Cohort

- Physical risks: Physical risks to subjects include if they feel reassured by the app's feedback/content and choose not to contact their care team for severe symptoms. It is also theoretically possible that patients are given medication advice that is either ineffective at relieving pain.
- Psychological risks: Reporting pain and psychological symptoms daily may be distressing for some patients. It may also be the case that reviewing psychological content may be distressing as awareness of cognitive and emotional factors relevant to pain will be acknowledged.

• Privacy risks: There is a risk of privacy violation or loss of confidentiality; however, this is anticipated to be minimal, and the study team is committed to guaranteeing adequate protection against risk as described in the following section.

9.5 Data to be collected:

- 9.5.1 Interview Data: Audio and video recordings of feedback will be collected from all interview participants regarding their perceived feasibility and acceptability of the mobile application as well as their experience with the app.
- 9.5.2 E-Acceptability (Survey) Data: Participants will complete an acceptability survey following review of finalized content (see Appendices I).
- 9.5.3 Chart Abstraction: Baseline demographic and clinical data will be collected from all patient participants via chart abstraction. Data will also be collected at the end of the pilot intervention. Data will include non-identifiable clinical/demographic information, including the following:
 - 9.5.3.1 Gender
 - 9.5.3.2 Age
 - 9.5.3.3 Ethnicity
 - 9.5.3.4 Race
 - 9.5.3.5 Cancer type
 - 9.5.3.6 Cancer stage
 - 9.5.3.7 Opioid medications
 - 9.5.3.8 Pain score during last visit (see Appendices O).
 - 9.5.3.9 Health service utilization (e.g. ED visits, hospitalizations, unplanned urgent clinic visits, changes to opioid medications, psychosocial oncology visits)
 - 9.5.4 Survey Assessment Data: Demographic, disease, medication, pain, mood, stress, and sleep data will be collected at baseline before the intervention, end of the 4week intervention, and at the end of the 2-week post intervention period (see Appendices P, Q, R). T1 and T2 of Table 5.
 - 9.5.5 Symptom Reporting: Individual pain, pain interference, pain medication use, stress, mood, and sleep symptoms as well as pain management data will be recorded for each participant over the course of the pilot intervention (Appendix U). Participants will report their symptoms and management daily and weekly.
- *9.6* **Long term follow-up:** Participants in the Pilot Cohort complete a survey assessment assessing quality of life, pain, psychological

measures, healthcare utilization, and app use at the end of the 2 weeks post-intervention (T3 of Table 5).

Measures collected via patient assessments			Survey		App data	Chart review
Assessment	Measure	T1	T2	T3		
Socio-demographics	Standard	Х				
Clinical characteristics	Standard					Х
Baseline cellphone use	MTUAS	х				
Pain	BPI	х	Х	х		
severity/interference						
Opioid use/adherence	Self-report	Х	х	Х		
Quality of life	FACT-G	Х	Х	Х		
Satisfaction	Novel metric		Х			
Use of STAMP+CBT	-		Х	Х	Х	
Usability	SUS		Х			
Management changes	-					Х
Healthcare utilization	-		Х	Х	Х	Х
Self-efficacy in	PROMIS	Х	Х			
managing symptoms						
Self-efficacy in	PROMIS	Х	Х			
managing medications						
Pain catastrophizing	PCS	Х	Х	Х		
Stress	PSS	Х	Х	Х		
Patient reported	PRO-	Х	х	Х		
outcomes	CTCAE					
Depression and	PROMIS	Х	х	х		
Anxiety						
Sleep Disturbance	PROMIS	X	X	Х		

Table 5: Measures collected from patients at each of three survey timepoints

10 Data and Specimen Banking*

10.1 This study does not involve any specimen collection/banking of any kind. Personal health information will be collected as part of the study. The consent form informs the participants that data collected for this study may be used in the future. By consenting, participants agree. Participants will not be asked to provide additional informed consent for the use of de-identified information in future research. There is no scheduled date on which the audio recording and transcription information and data that is being used or shared for this research will be destroyed, because research is an ongoing process. However, the video recorded data will be destroyed after manuscript publication. Patients will not provide any data on their

personal symptoms' reports; no specific patient symptom data will be collected.

- 10.2 All data collected during this study will be stored and used for future research. Any personal identifiers will be removed so that information cannot be linked back to a patient. For the patients engaging in qualitative interviews, their video recorded data will be destroyed after manuscript publication.
- 10.3 Investigators can request the data collected from this study for new research. Data may also be shared with outside non-profit academic investigators as well as with for-profit pharmaceutical investigators or commercial entities with whom Dana-Farber collaborates such as the University of Oklahoma Health Sciences Center, Stephenson Cancer Center. Requests must be sent to the study chair ([name]) and must be approved by the Dana-Farber IRB prior to sharing.

11 Data Management* and Confidentiality

- 11.1 Because interviews produce qualitative results, statistical analyses will not be employed for a portion of this study. The study team will review qualitative feedback from patients and find common themes related to app feasibility and acceptability. The study team will use the common themes derived from qualitative thematic analysis of the interview that review this feasibility study to guide further iterations of the application and study procedures for a future larger, efficacy study of the STAMP+CBT app.
- 11.2 Statistical analyses will be utilized in the pilot intervention portion of this study to ascertain feasibility and acceptability. We will measure time spent on the app per day and per week, completion rates for surveys and content review, and frequency of log-ons over the course of the pilot. The primary objective is to determine feasibility and acceptability of STAMP+CBT. Defined using precision analysis, we will consider the intervention to be feasible if >70% of subjects complete \geq 4 of the 6 pain-CBT modules and patients will complete 50% of surveys by the end of 4-weeks (completion of the 4-week intervention study period and completion of the 2-week post intervention period).^{40,41} A module will be considered complete if the participant engages in >70% of its content, including completing mHealth survey items, psycho-educational content, and app exercises. The intervention will be considered acceptable if >80% of the acceptability items are rated 4 or higher/5; lower ratings will lead to app refinements. Other feasibility measures will assess time to accrual, participation rates, and study retention and completion rates. Power calculation: With 10 patients, we will be able to estimate these proportions with margins of error (half of a 95% confidence

interval) of approximately 18% or less assuming that the feasibility threshold of 70% is reached. This margin of error is small enough so that proportion estimates relevant to study feasibility will be accurate and provide informative guidance for future, larger studies. Although power is not sufficient in this pilot, we will explore associations between levels of engagement and changes in pain severity/interference, opioid use, catastrophizing, sleep, mood, and pain self-efficacy.

- 11.3 The data the research team will access regarding app utilization will include; date and time of app log-ins, date of time of survey completion, survey responses, including clinical reporting of daily symptoms and medication usage, total app log-ins during intervention period, percent of surveys completed during intervention period, date time and frequency patients access external educational content.
- 11.4 PHI data will be collected using REDCap and the STAMP+CBT app.
 - 11.4.1 **REDCap:** For this study, data and patient consent will be collected using the Partners instance of REDCap (redcap.partners.org). In collaboration with the Harvard Catalyst | The Harvard Clinical and Translational Science Center, REDCap (Research Electronic Data Capture) is a free, secure, HIPAA compliant web-based application hosted by Partners HealthCare Research Computing, Enterprise Research Infrastructure & Services (ERIS). Vanderbilt University, with collaboration from a consortium of academic and non-profit institutional partners, develops this software application for electronic collection and management of research and clinical study data. Data collection is customized for each study or clinical trial by the research team with guidance from ERIS **REDCap** administrators. **REDCap** is built around HIPAA guidelines and is 21 CFR Part 11 capable.
 - 11.4.2 **STAMP+CBT app:** The final application will be HIPAA compliant and compliant with DFCI security and privacy standards. The application is built on the Insight Platform where data is secure on Microsoft Azure servers (see Appendix AA for further details on this application and Appendix AB for previous IRB approval research at the University of Oklahoma Health Sciences Center through their IRB).

Microsoft enterprise cloud services are also covered by FedRAMP assessments. Microsoft Azure and Microsoft Azure Government received a Provisional Authority to

Operate from the FedRAMP Joint Authorization Board; Microsoft Dynamics 365 U.S. Government received an Agency Authority to Operate from the US Department of Housing and Urban Development, as did Microsoft Office 365 U.S. Government from the US Department of Health and Human Services.

All data collected by the Insight Platform is encrypted during storage and in transit. The Insight platform has been approved for research at the University of Oklahoma Health Sciences Center through their IRB (See Appendix AB). Users of the OUHSC Insight Platform should confer with their institution's policies regarding restrictions associated with data collection and transfer between the Insight mobile application, Microsoft Azure servers, and users institutional servers. Data collected and stored by users is intended to be de-identified. Any data classified as PHI will require users institution to enter into an appropriate Business Associate Agreement.

Study specific procedures to maximize data security:

Controlled access: The REDCap and STAMP+CBT app administrators will set up all user accounts so that each user only has access to their own relevant participant data in a prototype model only.

Use of unique study ID numbers: REDCap automatically assigns unique study ID numbers to each new case.

Extensive training: All personnel involved in this study are required to complete and document completion of extensive protocol training. Furthermore, all research personnel are required to have valid certification of human subjects research training

Storage of Patient Research Data: All patient research data is subject to HIPAA regulations at the host institution.

Note: Interviews will be audio and video recorded using the HIPAA compliant platform, Zoom. The audio and video recordings will be stored in a password protected Dropbox business account. The audio recordings will be transcribed analysis of feedback. It is important to keep the facial features of patients in the videos as this provides important sociobehavioral analysis. To protect the identity of subjects, we will advise patients to modify their name on screen and use their initials when logging into zoom, instead of their full name. Patients' video recorded data will be destroyed after manuscript publication.

The STAMP+CBT app will use the Microsoft Azure cloud service with multilayered security for storage of research data collected (see appendix AA).

11.5 The staff at Dana-Farber will be responsible for monitoring the data for completion, accuracy, and compliance. All personnel involved in this study are required to complete and document completion of extensive protocol training. Furthermore, all research personnel are required to have valid certification of human subjects' research training.

12 Provisions to Monitor the Data to Ensure the Safety of Subjects*

This is a social behavioral research project, not a treatment protocol. The study involves minimal risk.

As such, the only adverse event that will be monitored and reported is psychological distress as determined by the treating oncologist or palliative care provider. For any patient who exhibits severe distress as result of the study procedures, the study research assistant will notify the patients' oncologist, palliative care provider, and/or social worker for appropriate response, including possible mental health referral if necessary. Furthermore, participants will be *reminded that participation is voluntary and can be stopped at any time for any reason. See the DSMP* (*Appendix N*) for more details.

12.1 Protection against physical risks: The study team has placed extensive protections against the aforementioned physical risks of the app. These protections significantly exceed the level of support and guidance that patients would receive with usual care. Moreover, patients' symptom reports will be reviewed daily by the study staff and shared with clinical nurse navigators that are part of the patients' care teams, which represents closer monitoring than usual care. Finally, the patient-facing app always instructs patients to contact their care teams and reminds them that the portal is not monitored continuously, or to call 911/go to an emergency room for medical emergencies. First, the application sets a low bar for instructing patients to contact their care teams for reported symptoms. This includes reporting any new pain, fever, new or worsening back pain, new or worsening chest pain, any pain rated > 8 out of a 0 to 10 scale (See table 2 for the detailed list). Moreover, if patients report moderate to severe pain levels that do not meet the previous criteria, in addition to receiving education about their pain management, they are also reminded that their care team wants to hear from them if they are concerned about their symptoms or if their symptoms are not improving. A link to their care team's number is included in the application. This level of support is much greater than what patients have usually with routine care.

- 12.2 Protection against psychological risks: if in the course of their participation patients raise significant emotional distress, the appropriate care team members i.e. nurse navigator, physician, midlevel provider will be contacted to make appropriate social work or mental health referrals. Similar to that of physical risks, this app provides closer monitoring than what is provided for usual care for psychosocial needs; In addition to instructing patients to call their care team for advice, the RA will share patient's elevated symptoms with a nurse navigator, already assigned to patients' care teams, for follow up. As such, these nurse navigators, will have access to all health records and including any documentation for this study included in EPIC.
- 12.3 Protection against privacy risks: To monitor the risk of loss of confidentiality/privacy, the study team has ensured that the STAMP+CBT app is HIPPA compliant and meet the privacy and security standards set by DF/HCC. In addition, all collected study data will be maintained in a secure location and personal identifiers will be removed.

12.4 To maximize data security, both REDCap and STAMP+CBT employ:

- User Privileges To ensure that users have access only to data and information that they are supposed to have within the application, user privileges are utilized within the software. Each user has their own account, and their user account will only have access to information that they themselves have created or to which administrators have granted them access.
- Password-protection & Authentication Both systems are password protected and implement authentication to validate the identity of end-users that log in to the system.
- Logging and Audit Trail Both systems maintain built-in audit trails that log all user activity and all pages viewed by every user.
- 12.5 Institutions will register eligible participants in the Clinical Trials Management System (CTMS) OnCore as required by DF/HCC Policy REGIST-101.

13 Withdrawal of Subjects*

- *13.1* Subjects who do not complete app onboarding within 3 weeks of study enrollment will be withdrawn from the research study without their consent.
- 13.2 These patients will be informed of their withdrawal from the study by study staff. The overall DF/HCC study PI, [name],

will make all decisions regarding early termination of the study. The study team will then notify all participants accordingly.

